1. SYNOPSIS

Protocol Number	APL2-202
Official Title	A Phase IIa, Open Label, Multiple Dose Study to Assess the Safety, Efficacy and Pharmacokinetics of Subcutaneously Administered APL-2 in Subjects with Paroxysmal Nocturnal Hemoglobinuria (PNH)
Protocol Version and Date	Version 3.0 31 January 2018
Compound	APL-2
Study Phase and Type	Phase IIa. Open-label, evidence of activity, safety, tolerability, pharmacokinetics (PK), multiple dose study.
Study Objectives	
The objectives of the study are to assess the safety, tolerability, efficacy and PK of multiple (SC) doses of APL-2 in subjects with paroxysmal nocturnal hemoglobinuria (PNH) who have not received treatment with eculizumab in the past.
 
An exploratory objective of the study is to assess the pharmacodynamics (PD) of multiple SC doses of APL-2 when administered to PNH patients.

Study Population	
Subjects will:
 
• be male and female (using contraception as specified in the protocol) and at least 18 years old• have a diagnosis of PNH
Number of Subjects	The study will be conducted alongside the ongoing Phase Ib study APL2-CP-PNH-204 (PADDOCK) to investigate APL-2 in PNH patients who have not previously received treatment with eculizumab. Safety and efficacy data from both studies will be used to support the data obtained in the Phase III confirmatory study. Up to 20 subjects will be enrolled to complete 28 days of dosing.

Inclusion Criteria

At Screening (unless otherwise specified)

- At least 18 years old (inclusive)
- Diagnosed with PNH (white blood cell (WBC) clone >10%)
- Lactose dehydrogenase (LD) ≥ 2 times the upper limit of normal
- Screening Ferritin \geq normal and Total Iron Binding Capacity (TIBC) \leq LLN based on central lab reference ranges. If a subject is receiving iron supplements at screening, the investigator must ensure that his/her dose has been stable for 8 weeks prior to enrolment and must be maintained throughout the study (see [Section 8.4.4](#))
- Last transfusion within 12 months prior to screening
- Platelet count of $>30,000/\text{mm}^3$ at the screening visit
- Absolute neutrophil count $>500/\text{mm}^3$ at the screening visit
- Women of child-bearing potential (WOCBP) must have a negative pregnancy test at screening and must agree to use protocol defined methods of contraception for the duration of the study
- Males must agree to use protocol defined methods of contraception and agree to refrain from donating sperm for the duration of the study
- Vaccination against Neisseria meningitides types A, C, W, Y and B, Streptococcus pneumoniae and Haemophilus influenzae Type B (Hib) either within 2 years prior to Day 1 dosing, or within 14 days after starting treatment with APL-2. Unless documented evidence exists that subjects are non-responders to vaccination as evidenced by titers or display titer levels within acceptable local limits
- Willing and able to give informed consent

Exclusion Criteria

- Prior eculizumab (Soliris®) treatment
- Active bacterial infection
- Hereditary complement deficiency
- History of bone marrow transplantation
- Concurrent severe aplastic anemia (SAA), defined as currently receiving immunosuppressive therapy for SAA including but not limited to cyclosporin A, tacrolimus, mycophenolate mofetil or anti-thymocyte globulin
- Participation in any other investigational drug trial or exposure to another investigational agent, device or procedure within 30 days

- Evidence of QTcF prolongation defined as >450 ms for males and >470 ms for females at screening Breast-feeding women
- History of meningococcal disease

Endpoints

Primary Safety Endpoint:

The primary safety endpoints of the study are the number and severity of treatment emergent adverse events (TEAEs) following administration of multiple doses of SC APL-2.

Primary Efficacy Endpoints:

- Change from baseline in LD
- Change from baseline in Haptoglobin
- Change from baseline in Hemoglobin (Hb)

Secondary Endpoints:

- APL-2 plasma concentrations (and pharmacokinetic (PK) parameters as appropriate)
- Change from baseline in Functional Assessment of Chronic Illness Therapy (FACIT) Fatigue Scale score
- Change from baseline in reticulocyte count
- Change from baseline in total bilirubin
- Change from baseline in Linear Analog Scale Assessment (LASA) for Quality of Life
- Number of red blood cell (RBC) transfusions per month

Exploratory PD markers include:

- Complement (CH50, AP50, and C3) levels
- C3 deposition on RBC cells
- Clonal distribution of PNH RBCs

Planned Dose Levels

The planned dose for this single cohort study will be a daily dose of 270 mg/day however from Part 2A onwards intra-subject dose escalation up to a dose of 360 mg/day may be permitted.

The dose was determined based on cumulative safety, PK, and PD data from ongoing studies in PNH patients.

Safety data from this study will be reviewed by the SMC on a regular basis.

Study Design

This is a Phase IIa, open-label, multiple dose, study in patients with PNH who have not received eculizumab (Soliris®) in the past. A single cohort is planned for evaluation.

The study will be conducted alongside the ongoing Phase Ib study APL2-CP-PNH-204 (PADDOCK) to investigate APL-2 in PNH patients who have not previously received treatment with eculizumab. Safety and efficacy data from both studies will be used to support the data obtained in the Phase III confirmatory study. Up to 20 subjects will be enrolled to complete 28 days of dosing (Part 1).

Safety will be assessed throughout the study; serial blood and urine samples will be collected for these assessments. Blood samples will be collected for the assessment of APL-2 PK. Additional samples for assessment of PD will also be collected.

The study will consist of four parts:

- Part 1: subjects will receive APL-2 for 28 days.
- Part 2A: subjects may continue to receive APL-2 for a further 56 days if there is evidence of clinical benefit following review of available safety, PK and PD data by the investigator and sponsor
- Part 2B: subjects may continue to receive daily APL-2 treatment for up to 364 days if there is ongoing evidence of clinical benefit following review of the available safety, PK and PD data.
- Part 3: Safety follow up

Screening will take place within 30 days prior to the start of dosing on Day 1.

Subjects will be entered into Part 1 of the study on Day 1 at a time designated by the PI. Research nurses or other appropriately qualified research personnel will administer the SC infusions for a minimum of 3 days (Days 1-3) until the research nurse considers that the subject is both capable and confident to conduct self-administration. The subject will continue to self-administer infusions at the clinic on those days when a clinic visit occurs (Day 8, 15 and 22) and at an off-site location convenient to the subject on all other days up to Day 28 in Part 1.

Following ongoing review of available safety, PK and PD data by the investigator and sponsor, subjects showing evidence of clinical benefit may progress to Part 2A and then to Part 2B of the study and continue to receive daily doses of APL-2 until Day 84 and then until Day 364. Doses will be self-administered by the subject throughout this period at an off-site location convenient to the subject with the exception of Days 29, 36, 43, 57, 71, 85, 113, 141, 169, 197, 225, 253, 281, 309, and 337 where dosing is performed by the subject at the clinical site. After the conclusion of the treatment period (Day 364), subjects will return to the clinical site for follow-up study procedures on Day 365, 379, and

393 and final study procedures at an Exit Visit on Day 414 See Study Flow Chart in [Section 2](#).

The planned length of participation in the study for each subject is approximately 444 days (14.5 months) from Day -30 through completion of the Day 414 Exit visit procedures).

2. STUDY FLOW CHART

Study Period	Part 1 – Treatment (Daily from Day 1 to Day 28)										
	Study Week	1			2		3		4		
	Study Day	1	2	3	4 to 7	8	9 to 14	15	16 to 21	22	23 to 28
Informed Consent	x										
Demographics	x										
Medical, transfusion, and thrombosis history	x										
Vaccination. A								x			
Review entry criteria		x									
Preventive antibiotic. B		x	x	x	x	x	x	x	x	x	x
Physical examination. C	x										
12-lead electrocardiogram. D	x	x		x		x		x		x	
APL-2 administration. E		S	S	S	H	S	H	S	H	S	H
Injection site assessment. F		x	x	x	x	x	x	x	x	x	x
Concomitant medications	x	x	x	x	x	x	x	x	x	x	x
Vital sign measurements. G	x	x	x	x	x	x	x	x	x	x	x
Urinalysis	x	x				x		x		x	
Blood. I	x	x				x		x		x	
Pharmacokinetics. I		x (I)	x	x		x				x	
Anti-APL-2 Ab assay		x						x			
Hematology and chemistry.	x	x				x		x		x	
Coagulation profile	x	x				x		x		x	
Complement profile (C3, CH50 and AP50)	x	x				x		x		x	
Flow cytometry for PNH/C3 deposition	x	x				x		x		x	
Plasma Hb	x	x				x		x		x	
Pregnancy (B-human chorionic gonadotropin)	x										
Urine pregnancy test. J		x				x		x		x	
FACIT fatigue Scale		x						x			
LASA QoL		x						x			
Adverse events		x	x	x	x	x	X	x	X	x	x
Thrombosis record (MAVE). K		x	x	x	x	x	X	x	X	x	x

See footnotes below continuation flow chart

Study Period	Part 2A - Treatment (Daily from Day 29 to Day 84)											
	Study Week		5		6		7 and 8		9 and 10		11 and 12	
	Study Day		29	30 to 35	36	37 to 42	43	44 to 56	57	58 to 70	71	72 to 84
Informed Consent												
Demographics												
Medical, transfusion, and thrombosis history												
Vaccination. A												
Review entry criteria												
Preventive antibiotic. B	X	X	X	X	X	X	X	X	X	X	X	
Physical examination. C	X							X				
12-lead electrocardiogram. D	X		X		X		X		X		X	
APL-2 administration. E	S	H	S	H	S	H	S	H	S	H		
Injection site assessment. F	X	X	X	X	X	X	X	X	X	X	X	
Concomitant medications	X	X	X	X	X	X	X	X	X	X	X	
Vital sign measurements. G	X	X	X	X	X	X	X	X	X	X	X	
Urinalysis	X		X		X		X		X		X	
Blood. I	X		X		X		X		X		X	
Pharmacokinetics. I	X					X				X		
Anti-APL-2 Ab assay	X									X		
Hematology and chemistry.	X		X		X		X		X		X	
Coagulation profile	X		X		X		X		X		X	
Complement profile (C3, CH50 and AP50)	X		X		X		X		X		X	
Flow cytometry for PNH/C3 deposition	X		X		X		X		X		X	
Plasma Hb	X		X		X		X		X		X	
Urine pregnancy test. J	X		X		X		X		X		X	
FACIT fatigue Scale	X					X				X		
LASA QoL	X					X				X		
Adverse events	X	X	X	X	X	X	X	X	X	X	X	
Thrombosis record (MAVE). K	X	X	X	X	X	X	X	X	X	X	X	

See footnotes below continuation flow chart

Study Period	Part 2B - Treatment (Daily from Day 85 to Day 364) (L)												
	Study Week	13 to 16		17 to 20		21 to 24		25 to 28		29 to 32		33 to 36	
	Study Day	85	86 to 112	113	114 to 140	141	142 to 168	169	170 to 196	197	198 to 224	225	226 to 252
Vaccination	X												
Preventive antibiotic. B	X	X	X	X	X	X	X	X	X	X	X	X	X
Physical examination. C	X												
12-lead electrocardiogram. D	X		X		X		X		X		X		X
APL-2 administration. E	S	H	S	H	S	H	S	H	S	H	S	H	S
Injection site assessment. F	X	X	X	X	X	X	X	X	X	X	X	X	X
Concomitant medications	X	X	X	X	X	X	X	X	X	X	X	X	X
Vital sign measurements. G	X	X	X	X	X	X	X	X	X	X	X	X	X
Urinalysis	X		X		X		X		X		X		X
Blood. I	X		X		X		X		X		X		X
Pharmacokinetics. I	X		X		X		X		X		X		X
Anti-APL-2 Ab assay	X				X				X				
Hematology and chemistry.	X		X		X		X		X		X		X
Coagulation profile	X		X		X		X		X		X		X
Complement profile (C3, CH50 and AP50)	X		X		X		X		X		X		X
Flow cytometry for PNH/C3 deposition	X		X		X		X		X		X		X
Plasma Hb	X		X		X		X		X		X		X
Urine pregnancy test. J	X		X		X		X		X		X		X
FACIT fatigue Scale	X				X				X				
LASA QoL Scale	X				X				X				
Adverse events	X	X	X	X	X	X	X	X	X	X	X	X	X
Thrombosis record (MAVE) K	X	X	X	X	X	X	X	X	X	X	X	X	X

See footnotes below continuation flow chart

Study Period	Part 2B - Treatment (Daily from Day 85 to Day 364) (L)								
	Study Week	37 to 40		41 to 44		45 to 48		49 to 52	
	Study Day	253	254 to 280	281	282 to 308	309	310 to 336	337	338 to 364
Informed Consent									
Review entry criteria									
Preventive antibiotic. B	X	X	X	X	X	X	X	X	X
Physical examination. C	X							X	
12-lead electrocardiogram. D	X		X			X		X	
APL-2 administration. E	S	H	S	H	S	H	S	H	
Injection site assessment. F	X	X	X	X	X	X	X	X	X
Concomitant medications	X	X	X	X	X	X	X	X	X
Vital sign measurements. G	X	X	X	X	X	X	X	X	X
Urinalysis	X		X		X		X		
Blood. I	X		X		X		X		
Pharmacokinetics. I	X		X		X		X		
Anti-APL-2 Ab assay	X				X				
Hematology and chemistry.	X		X		X		X		
Coagulation profile	X		X		X		X		
Complement profile (C3, CH50 and AP50)	X		X		X		X		
Flow cytometry for PNH/C3 deposition	X		X		X		X		
Plasma Hb	X		X		X		X		
Urine pregnancy test. J	X		X		X		X		
FACIT fatigue Scale	X				X				
LASA QoL Scale	X				X				
Adverse events	X	X	X	X	X	X	X	X	X
Thrombosis record (MAVE). K	X	X	X	X	X	X	X	X	X

See footnotes below continuation flow chart

Study Period	Part 3 – Follow-up and Exit. (M)				
	Study Week	53	55	57	60
	Study Day	365	379	393	414
Informed Consent					
Review entry criteria					
Preventive antibiotic. B	X	X			
Physical examination. C	X			X	
12-lead electrocardiogram. D	X				
APL-2 administration. E					
Injection site assessment. F	X				
Concomitant medications	X	X	X	X	
Vital sign measurements. G	X	X	X	X	
Urinalysis	X	X	X	X	
Blood. I	X	X	X	X	
Pharmacokinetics. I	X	X	X	X	
Anti-APL-2 Ab assay	X			X	
Hematology and chemistry.	X	X	X	X	
Coagulation profile	X	X	X	X	
Complement profile (C3, CH50 and AP50)	X	X	X	X	
Flow cytometry for PNH/C3 deposition	X	X	X	X	
Plasma Hb	X	X	X	X	
Urine pregnancy test. J	X		X	X	
FACIT fatigue Scale	X		X	X	
LASA QoL Scale	X		X	X	
Adverse events	X	X	X	X	
Thrombosis record (MAVE) K	X	X	X	X	

See study flow chart footnotes on next page

FOOTNOTES:

- A. If required i.e. not previously vaccinated subjects will receive vaccinations against *Neisseria meningitidis* types A, C, W, Y and B, *Streptococcus pneumoniae* and *Haemophilus influenzae* Type B (Hib). If the subject's first documented *Neisseria meningitidis* vaccine/s are administered at Day 15, a booster (for both vaccinations) should be administered after 2 months. If Pneumococcal vaccination is required, a dose of PCV13 will be administered at Day 15 and a dose of PPSV23 will be administered at least 8 weeks later (unless documented evidence exists that subjects are non-responders to vaccination as evidenced by titers or display titer levels within acceptable local limits). The PI will discuss with the Sponsor in regard to specific patient requirements
- B. Preventive antibiotics will be prescribed from Day 1. Antibiotics will be taken from Day 1 until 14 days after the first dose of APL-2. Specifically:
 - Day 1 to Day 14: Ciprofloxacin 500 mg twice daily (take post dose ECG before Ciprofloxacin is administered on days 1).
 - Day 15 onwards: Penicillin V 500 mg twice daily.
- C. Full physical examination will be performed at the scheduled time points indicated. A symptom-driven physical examination may be performed at other times, at the PI's discretion.
- D. If done on a dosing day, electrocardiograms (ECGs) are to be performed within 30 minutes after dosing.
- E. S = Administration at clinical site. H = Administration at subject's home, workplace, or other location convenient to the subject. Treatment may be stopped at any time if the investigator and sponsor conclude that there is no demonstration of clinical benefit to continue APL-2 administration past this point.
- F. Injection site assessment will be performed within 30 minutes after APL-2 administration. Ambulatory syringe infusion pump training will include instructions to report any injection site reaction to the PI.
- G. At clinic visits, vital signs will be measured within 2 hours prior to dosing and within 30 minutes after dosing. When APL-2 is self-administered, pre- and post-dose vital signs will not be measured.
- H. Reserved – See note E.
- I. If done on a dosing day, blood samples will be taken pre-dose with the exception that on Day 1 only a pharmacokinetic sample will be taken pre-dose and at a minimum of 2.5 hours post-dose or immediately prior to discharge from the clinic (if subject is kept at the clinic longer than 2.5 hours).
- J. If done on a dosing day, urine pregnancy test should be completed for WOCBP prior to dosing.
- K. MAVE = Major Adverse Vascular Event. Ambulatory syringe infusion pump training will include instructions to report any events to the PI.
- L. If dose is increased during Part 2B, subjects will come back to the clinical site for safety visits every other week for the first 6 weeks of the dose change. These visits may alternate with the monthly visits and should be recorded as unscheduled visits. The same procedures listed under the monthly visits will be performed.
- M. Subjects that discontinue dosing at any time during Part 1, 2A or 2B will move directly into Part 3 for safety follow up visits.

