4.3 Risk/Benefit

A number of safety monitoring practices are required by this protocol (i.e. physical examination, vital signs, 12-lead ECG, hematology, serum chemistry, urinalysis, coagulation, prompt reporting of pre-defined AEs of special interest, and AE questioning) in order to protect the subjects' safety.

Injection/infusion site and pump use safety will be assessed during clinical visits, and any significant finding from the assessment will be reported as an AE (see [Section 11](#)).

The volume of blood planned for collection from each subject over the course of the study (see [Section 10.6](#)) will be minimized, in order to minimize the impact on the overall health of these anemic subjects. If dose is increased during part 2B, additional blood draws will be required.

Systemic complement inhibition might predispose individuals to infections caused by encapsulated organisms, including *Streptococcus pneumoniae*, *Neisseria meningitides*, and *Haemophilus influenzae*. Prophylactic antibiotic therapy (ciprofloxacin 500 mg BID) will be prescribed to all subjects from Day 1 (commencing after first administration of APL-2 and the subsequent post-dose PK sample and ECG) to Day 14. At Day 15 all subjects will discontinue treatment with ciprofloxacin and receive vaccinations, if required, against *Streptococcus pneumoniae*, *Neisseria meningitides A, C, W, Y and B*, and *Haemophilus influenzae*. Prophylactic antibiotic therapy (penicillin V 500 mg twice a day) will be prescribed to all subjects from Day 15 and will be taken by subjects until 14 days after the final dose of APL-2 to minimize potential infection risk. Body temperature and vital signs will be monitored periodically and relevant blood parameters monitored regularly throughout the study to assess for signs of infection. The principal investigator (PI) should be contacted immediately in the event of a suspected infection despite prophylactic antibiotic treatment for guidance and appropriate action to be taken.

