8.4 Concomitant Medications

8.4.1 Prophylactic antibiotics

Prophylactic antibiotic therapy will be prescribed to all subjects to minimize potential infection risk. Prophylactic antibiotics will be initiated on day 1 following administration of APL-2 dosing and continue until 2 weeks after the last dose.

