8.4.1.2 Primary prophylactic antibiotic Day 15 onwards

- Penicillin V 500 mg twice daily

Serious and occasionally fatal hypersensitivity (anaphylactic) reactions have been reported in patients on beta-lactam antibiotic (e.g. penicillin, amoxicillin, etc.) therapy. These reactions are more likely to occur in individuals with a history of penicillin hypersensitivity. Before initiating therapy with penicillin V, careful inquiry should be made concerning previous hypersensitivity reactions to penicillins or cephalosporins. If subjects have a known hypersensitivity to penicillin/amoxicillin they may be prescribed an alternative antibiotic at the outset.

Other frequently reported adverse effects in patients taking penicillin are diarrhea/loose stools, nausea, skin rashes and urticaria, and vomiting. Patients should, therefore, be advised that these reactions may occur.

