9.2 Part 1 - Treatment Period – (Days 1 to 28)

Subjects will receive daily SC doses of APL-2 on Days 1 to 28. APL-2 will be administered at the clinical site by study personnel during the first 3 days and thereafter by the subject under supervision whilst at the clinical site or off-site self-administered by the subject. Subjects will be trained to prepare and administer their infusions of APL-2, complete the administration diary and injection site assessment.

9.2.1 On Site Administration (Day 1 to Day 3 and Days 8, 15 and 22)

The first 3 daily SC doses of APL-2 (Day 1 to 3) will be administered by study personnel. Doses on 8, 15 and 22 will be administered, by the subject under supervision, at the clinical site. Subjects will remain in the clinic for at least 2.5 hours after receiving the first dose of APL-2 on Day 1.

If required subjects will receive vaccinations on Day 15 with boosters scheduled appropriately. Antibiotic therapy will be changed from ciprofloxacin to penicillin V.

Blood samples for laboratory analysis, PK/PD, and antigenicity will be taken during site visits as outlined in the Study Flow Chart in [Section 2](#).

Specific procedures for each visit are listed in the Study Flow Chart.

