## 5.8 Protocol Deviations

Protocol deviations will be recorded by the site separately from the clinical database. The CRO/Apellis will classify major and minor protocol deviations per the agreed protocol deviation management plan. The Apellis study team will review the protocol deviations and their classification throughout the study and before database lock.

Confirmed major and minor protocol deviations will be documented in the Protocol Deviation tracker for the study. Major/minor protocol deviations will be listed for the Safety Set.

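### Flow-chart footnote B ends antibiotic prophylaxis 14 days after the first dose of APL-2, contradicting the rest of the footnote, its grid row and Protocol Sections 4.3, 8.4.1, 8.4.1.2 and 9.2.1

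*Protocol*

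**What the plan says.** Footnote B of the Study Flow Chart (Protocol Section 2) states: "Antibiotics will be taken from Day 1 until 14 days after the first dose of APL-2". Its second bullet, two lines lower, reads: "Day 15 onwards: Penicillin V 500 mg twice daily". The row that carries the footnote, "Preventive antibiotic. B", is marked throughout Parts 1, 2A and 2B and at the Part 3 visits on Days 365 and 379. It is blank at Days 393 and 414.

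Elsewhere in the protocol:

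- Section 4.3 (Risk/Benefit) says that the antibiotic given from Day 15 "will be taken by subjects until 14 days after the final dose of APL-2".
- Section 8.4.1 has prophylaxis start on Day 1 and "continue until 2 weeks after the last dose".
- Section 8.4.1.2 is headed "Primary prophylactic antibiotic Day 15 onwards".
- Section 9.2.1, describing the Day 15 visit, says: "Antibiotic therapy will be changed from ciprofloxacin to penicillin V".

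SAP Appendix 17.1 reproduces the flow chart and footnote B, including the first-dose sentence. SAP Section 5.8 has deviations graded as major or minor and then says: "Major/minor protocol deviations will be listed for the Safety Set".

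**The concern.** The footnote sentence counts its 14 days from the first dose. Sections 4.3 and 8.4.1 count the same interval from the last dose. Taken literally, the two rules give different stop days for anyone dosed more than once, and daily dosing may run to Day 364.

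Two things are at stake. The first is subject protection. Section 4.3 explains that inhibiting complement may make subjects more prone to certain bacterial infections and gives prophylaxis as the measure to limit that risk. Section 11.5 makes infection of any origin an adverse event of special interest. Section 9 sends sites to the flow chart for the schedule, and footnote B is the only text in the chart on how long prophylaxis lasts. The one end point it states is the conflicting one.

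The second is the deviation review. The same antibiotic record could comply with one passage and deviate from another.

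**Working it through.** The documents give no figure to reproduce. The check is study-day arithmetic followed by a comparison of the passages.

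**Inputs**

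- First dose: Day 1 (Protocol Section 8.3.2).
- Last dose for a subject who stops at the end of a part: Day 28, 84 or 364 (Protocol Sections 9.2 to 9.4).
- Interval: 14 days in footnote B and Section 4.3; 2 weeks, the same length, in Section 8.4.1.

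**Formula:** stop day = day of the anchor dose + 14.

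First-dose anchor (footnote B sentence): 1 + 14 = Day 15 for every subject.

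| Last dose | Stop, last-dose anchor | Gap from Day 15 | Dosing days after Day 15 |
|---|---|---|---|
| Day 28 | 28 + 14 = Day 42 | 42 − 15 = 27 days | 28 − 15 = 13 of 28 (46.4%) |
| Day 84 | 84 + 14 = Day 98 | 98 − 15 = 83 days | 84 − 15 = 69 of 84 (82.1%) |
| Day 364 | 364 + 14 = Day 378 | 378 − 15 = 363 days | 364 − 15 = 349 of 364 (95.9%) |

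The last column describes the footnote sentence read alone. Footnote B read as a whole does not leave those days without prophylaxis, because its second bullet continues from Day 15.

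**The passages compared with a Day 15 stop**

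- Direct conflict, because a different anchor is stated: Sections 4.3 and 8.4.1.
- Conflict because prophylaxis continues past Day 15, with no stop time stated: the footnote's second bullet, the heading of Section 8.4.1.2, and Section 9.2.1, where the antibiotic is changed and not ended.
- Conflict through the grid: the row is marked in the treatment columns after Day 15 and at two follow-up visits. The last mark, Day 379, is 379 − 364 = 15 days after a Day 364 dose, one day past Day 378. Part 3 columns exist only for visits, so the mark does not itself state a stop day. It cannot fit a stop at Day 15.

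No other passage in the protocol counts the stop from the first dose. The SAP appendix sentence is a copy of the same error, not a second one.

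**The case against.** The strongest reply is that this is one wrong word, corrected by its own context. The sentence leads straight into a bullet for Day 15 onwards, the Day 15 visit instruction is to switch antibiotic, and the row is marked to the end of treatment. A site following the whole footnote could not stop at Day 15. On that view the gaps above measure a reading nobody would adopt. That stands as a limit on the size of the problem: the figures show how far apart the two rules are, not an expected loss of cover. It does not remove the need to correct the sentence. The second bullet gives no end day, so the only end point written in the chart remains the conflicting one. Nor does the grid settle the matter for every subject. Under footnote M, those who discontinue at any time go directly into Part 3, whose columns are labelled only Days 365 to 414. Their stop day has to be worked out from the text.

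It can also be said that SAP Section 5.8 relies on a deviation management plan that is not among these documents and may already fix a reference. That is fair. The effect on deviation grading is therefore possible, not shown, and is confined to a listing for 4 subjects.

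Finally, enrollment closed at the end of 2018 and the SAP is dated 17 July 2019, so Day 15 had very probably passed for all 4 subjects. A correction at the SAP date could not alter what happened on that day. A last-dose stop could still have been ahead: Day 364 falls 363 days after Day 1, so a subject who started after 19 July 2018 and completed treatment would have taken the last dose after the SAP was issued. The documents do not give the start dates.

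**Conclusion.** The contradiction is real and stands in current protocol text. The footnote sentence gives Day 15. The last-dose wording gives Day 42, 98 or 378, a difference of 27, 83 or 363 days according to when dosing ends. These figures assume a first dose on Day 1 and a last dose on the final day of Part 1, 2A or 2B.

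The surrounding text makes a drafting slip the likely explanation, but which stop time is intended is for the sponsor's medical team to confirm.

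No planned analysis changes. The study is descriptive, 4 subjects were enrolled, and concomitant medications and treatment-emergent adverse events are listed by subject. The point should be fixed because it concerns a protective measure in the schedule that sites use, and because deviations need one reference.

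**What to change.** Reconcile the sentence in footnote B of the protocol flow chart with the second bullet, the grid row and Sections 4.3, 8.4.1, 8.4.1.2 and 9.2.1, so that no two passages imply different stop times. Sections that state no stop time need none added, provided they agree with the rule that is confirmed. The sponsor's medical team must say which stop time is intended.

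Make the same correction to the copy in SAP Appendix 17.1. Before database lock, record the confirmed stop time as the reference for grading prophylaxis deviations under SAP Section 5.8, or confirm that the deviation management plan already does so.

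The cost is one line in the protocol, by clarification letter or amendment, the same line in the SAP appendix, and a note for the deviation review. No new data are needed and no planned output changes.
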